Visit Day 3: Habituation and Fear Conditioning. On visit 3, participants will be asked to complete habituation and fear conditioning phases of the fear conditioning, extinction, and recall paradigm (18, 19, 45, 53, 54, 57). This task involves the computerized presentation of photographs of two different rooms, one serving as the fear acquisition context (CX+; picture of an office) and one as the fear extinction context (CX-; picture of a bookcase) in which two conditioned stimuli (CS+; red and blue light) and one never-to-be conditioned stimulus (CS-; yellow light) will be presented. One CS+ will be extinguished during extinction (CS+E) and the other will not (CS+U). See Figure above at right. Experimental scripts will run in E-Prime, and for all trials during each of four task phases - habituation, conditioning, extinction learning and extinction retention - the CX (+/-) will be presented for 9s: 3s alone, followed by 6s in combination with the CS (+/-) with a 15s average inter-trial interval (12-18s). During each of the four task phases two electrodes will be placed over the second digits of the index and middle fingers of the dominant hand, which may or may not deliver an annoying, but non-harmful electrical shock acting as unpleasant, unconditioned stimulus (US). Before each task phase, except habituation, participants will be instructed that they "may or may not be shocked," and to "pay attention to any patterns you observe between the image that you see and whether or not it is followed by a shock," Participants will also be instructed that "if you observe a pattern, it will hold throughout the session and the rest of the experiment." Participants will not be explicitly informed of the CS/US contingency.

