Prior to starting habituation, participants will individually select electric shock intensity to be "highly annoying but not painful" as the US, following previously used procedures in our lab (53, 54). During habituation participants will be told that the purpose of this phase is to familiarize them with all possible pictures in the experiment, and that no shock would be delivered. Participants will see all stimuli (i.e. to-be CS+E, CS+U, CS-) once in both contexts (CX+ and CX-). After habituation participants will undergo fear conditioning. A total of 32 trials: eight CS+E, eight CS+U, and 16 CS- trials will be presented across two blocks in the CX+ only. Both CS+ trials will be paired with US at a 60% reinforcement rate. The US will occur immediately after CS+ offset. After fear conditioning, participants will complete contingency ratings and the PANAS to assess general affect. Habituation and fear conditioning will either occur at Butler Hospital or in the simulation scanner at the MRF. This visit will last approximately one hour.

Visit Day 4: Extinction of Conditioned Fear. Visit 4 will need to occur 24 hours after visit 3, with an allowable deviation of 4 hours. Extinction learning will either occur at Butler Hospital or in the simulation scanner at the MRF. Participants will be reminded of the instructions and receive either 1) active tDCS during extinction learning, or 2) active tDCS immediately following extinction learning, or 3) sham stimulation according to the randomization schedule. Regardless of randomization group, all participants will be asked to repeat completion of Day 1 tDCS safety screening and tDCS equipment will be placed on the scalp before beginning the task. During the extinction phase a total of 12 trials: six CS+E and six CS- trials will be presented solely in the CX- and no shocks will be delivered. Median split will determine the latter three CS+E trials as 'late extinction' trials. After extinction and tDCS procedures, participants will complete contingency ratings and the PANAS to assess general affect. This visit will last approximately one hour.

Day 5: Extinction Retention and Fear Renewal. Visit 5 will need to occur 24 hours after visit 4, with an allowable deviation of 4 hours. The extinction retention and renewal phases serve as the test phase and

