will either be administered at Butler Hospital or in the real MRI scanner at the Brown MRF. Prior to starting extinction retention, participants will be reminded of the instructions. A total of 32 trials: eight CS+E, eight CS+U, and 16 CS- trials within the CX- only will be presented and no shocks will be delivered. Early recall retention will be based on the first four CS+E and first four CS+U trials. After extinction retention, participants will complete contingency ratings and undergo a fear renewal phase. During fear renewal participants will see the same content as during fear conditioning, but no finger shocks will be delivered. After fear renewal participants will complete contingency ratings and the PANAS to assess general affect. This visit will last approximately one hour.

Skin Conductance. Skin conductance will be recorded for 2 minutes prior to each fear conditioning, extinction and recall phase to establish a physiologic baseline, and continuously throughout each phase. Baseline skin conductance level will be used as a covariate in analysis. To assess skin conductance, two MRI-compatible electrodes will be placed on the thenar eminence of the non-dominant hand, as we will be assessing skin conductance in both the simulator and real scanner depending on task phase as described above. Skin conductance reactivity (SCR) will be quantified by the phasic response that occurs after the presentation onset of each CS+/- stimulus following previous guidelines (57) and our prior work (53, 54). The first trial during fear conditioning will be removed from analyses to avoid the influence of an orienting response on the data. Because of the effects of nicotine and caffeine on SCR we will ask people not to consume nicotine or caffeine two hours prior to the start of the study.

Transcranial direct current stimulation. Device: Continuous direct current stimulation will be delivered by a CE-certified tDCS device (NeuroConn).

tDCS Electrode Montage: We will use a conventional 1 (anode) x 1 (cathode) midline bipolar-non balanced electrode montage (68) with the anode placed approximately over FP1 of the 10-20 EEG coordinate system and the cathode over P10.

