Rationale: To determine the ideal electrode montage, participants will undergo a structural MRI scan (with acquisition settings optimized for modeling inputs) on Day 2 to inform finite element modeling (69). Initial electrical field modeling of the proposed montage was obtained using tDCS Explore by Soterix Medical (v.4.0, New York, NY). This modeling will be confirmed based on individual neuroanatomy MRI scans obtained on Day 1 using SimNIBS software (v2.0, DMCR, Germany) and electrode montage will be adjusted as necessary in collaboration with the Neuroimaging and Neuromodulation Core. Electrodes will be placed at FP1 and P10 and might be adjusted (by Drs. [name] and [name]) based on the latter individualized modeling to target VMPFC region. Using this approach, we anticipate at least 0.25-0.35 V/m will reach the VMPFC. Prior tDCS research has demonstrated that tDCS effects in this order of magnitude have effects on brain functioning (70).

Dose Parameters: Active tDCS will consist of approximately 15 minutes 2 mA intensity through 3x3 cm (9 cm²) or 5x5 cm (25 cm²) electrodes, resulting in a maximum 2.22 A/m² current density, with an additional 30s ramp up/down at the beginning and end of stimulation, respectively. Active tDCS will be applied either during extinction learning or immediately after extinction learning. This duration is selected based on task duration and allows an additional 2 minutes of tDCS prior to the start of extinction learning. Sham stimulation will be applied for the remainder, namely after or during extinction learning respectively. Sham stimulation parameters – 1 mA for 30s, with a ramp up/down over 30 sec each – are selected to mimic the scalp sensation of active tDCS without prolonged intense stimulation.

Rationale: 2 mA intensity was chosen based on research showing that more intense stimulation protocols may result in stronger effects on the brain (71) and cognition (72).

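### The stated 15-minute stimulation, the 12-trial extinction task and the sham assigned after extinction cannot all hold, and the end of active current in the during-extinction arm is not stated

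*Combined protocol and SAP*

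**What the plan says.** Section 2.C3, Dose Parameters, states: "Active tDCS will consist of approximately 15 minutes 2 mA intensity", with 30 s ramps added at each end. It gives the reason for the length: "This duration is selected based on task duration and allows an additional 2 minutes of tDCS prior to the start of extinction learning". It then assigns sham to whichever period is not active. Section 2.C2 says the same: the arm stimulated during extinction receives sham during consolidation.

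The task is described under the visit days of Section 2.C3. For all four phases (Visit Day 3), the context picture "will be presented for 9s: 3s alone, followed by 6s in combination with the CS (+/-) with a 15s average inter-trial interval (12-18s"). For Visit Day 4: "During the extinction phase a total of 12 trials: six CS+E and six CS- trials will be presented solely in the CX" (the extinction context). The scoring rule fits that count: "Median split will determine the latter three CS+E trials" as late extinction, which is half of six. The retention phase is longer: "A total of 32 trials: eight CS+E, eight CS+U, and 16 CS- trials within the CX- only will be presented".

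The tDCS Procedures paragraph starts the first block 2 minutes before extinction and runs it through that phase, with no stop time. For the post-extinction arm, active current begins as soon as the last extinction trial is over. No second-block start is given for the other two arms.

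**The concern.** Timing of stimulation is the factor under study. Aims 1 and 2 predict that current delivered after extinction does better than current delivered during extinction, and better than sham. The Background singles out the period right after extinction as the relevant window. The after-versus-during comparison therefore depends on which active minutes fall in which window.

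The stated duration is more than twice what the described task needs. A reader cannot tell whether the during-extinction arm also receives current in the consolidation window, receives a shorter dose than the other active arm, or performs a longer task than the one described. These have different consequences: a blurred timing contrast, timing mixed with dose, or no effect on inference.

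**Working it through.** **Inputs.** Active duration about 15 min, lead-in 2 min and current 2 mA (2.C3, Dose Parameters). Twelve extinction trials (2.C3, Visit Day 4). Trial 9 s plus interval 12–18 s, mean 15 s (2.C3, Visit Day 3).

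**Task length implied by the rationale.** 15 − 2 = 13 min. Spread over 12 trials this is 13 × 60 / 12 = 65 s per trial, against 21–27 s specified. At 24 s per trial it is 13 × 60 / 24 = 32.5 trials.

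**Task length as specified.** 12 × (9 + 15) s = 288 s = 4.8 min. Limits: 12 × 21 = 252 s (4.2 min) and 12 × 27 = 324 s (5.4 min). With the lead-in: 6.8 min (6.2–7.4). The stated 15 min is not reproduced.

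**Can other elements close the gap?** Counting both ramps (1 min) gives 7.8 min. The protocol also says: "Skin conductance will be recorded for 2 minutes prior to each fear conditioning, extinction and recall phase". If that baseline were separate from the lead-in and run under current (an assumption), the total with ramps is 9.8 min, and 5.4 + 2 + 1 + 2 = 10.4 min at most. None of these reaches 15, and the ramps are described as extra to the 15 min in any case.

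**What each resolution implies.**

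- *Twelve trials, full 15 min from the lead-in.* 15 − 6.8 = 8.2 min (7.6–8.8) of the during-extinction arm's active current follows the last trial. That is 8.2 / 15 = 55% of it. Charge is 2 mA × 900 s = 1.80 C in both active arms. The sham-after-extinction statement then fails.
- *Twelve trials, current stops with the task.* Active minutes are 6.8 and 15, a ratio of 15 / 6.8 = 2.2 (2.0–2.4). Charge excluding ramps is 2 mA × 408 s = 0.82 C against 1.80 C. The 15-minute figure then fails for one arm.
- *About 32 trials, as in conditioning and retention.* 32 × 24 s = 12.8 min, and 14.8 min with the lead-in (13.2–16.4). This matches the stated duration, but the total of 12, the six/six split and the rule for late extinction then all fail.

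**Sensitivity.** With an extra 2-minute baseline under current, lead-in plus task is 8.8 min. The overlap in the first case falls to 15 − 8.8 = 6.2 min, and the ratio in the second to 15 / 8.8 = 1.7.

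**The case against.** The duration is called approximate. A length based on the task may simply mean one long enough to cover it plus the lead-in, which 15 minutes is. That is fair, and it could save the rationale sentence. It does not reconcile a 15-minute active block with sham after a 4.8-minute task.

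The overlap case also fits the text poorly. Both the design section and the dose section assign sham after extinction to that arm. Its first block would still be running for about 8 minutes at the moment the post-extinction arm's second block begins, which sits badly with blinding by device presets unless one preset spans both periods. This stands as a reason not to presume overlap. Equally, the dose section gives that arm no shorter duration.

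The consequence depends on the task script and the presets, which are not in the documents. One resolution is harmless, so no damage to inference has been shown. That also stands.

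Three stronger readings are tempting and not supported:

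- A reader might infer that either the duration or the trial count must be wrong. In the overlap case both are right and the sham assignment is wrong. The trial timing or the rationale could also be the error.
- A reader might infer that overlap leaves 6.8 / 15 = 45% of the planned contrast. Let b be the benefit per post-extinction minute and d the benefit of stimulation during extinction. The fraction is (6.8b − d) / (15b − d), which is 45% only if d = 0. With d = 3.4b it is 29%, and with d above 6.8b the numerator is negative. The Background reports a benefit of stimulation during extinction in healthy controls, so d = 0 cannot be assumed.
- A reader might infer that the arms were in fact contaminated or unequally dosed. The documents do not show what was delivered.

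**Conclusion.** The inconsistency is firm. As specified, lead-in plus task lasts 6.8 minutes (6.2–7.4), against about 15 stated. At least one of five statements is wrong as written: duration, trial count, trial timing, rationale, or sham after extinction in the during-extinction arm. The missing stop time leaves the matter open.

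The effect on inference is conditional and limited to after-versus-during. With overlap, the contrast is blurred by an amount the documents do not allow to be quantified. If post-extinction current is what helps, the pull is toward no difference. With early stopping, timing is confounded with a roughly two-fold dose difference, which favours the post-extinction arm if more minutes help. With about 32 trials, inference is intact. After-versus-sham is unaffected throughout.

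The figures take 15 minutes at face value, although it is stated as approximate, and use the stated interval limits as outer bounds.

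**What to change.** 1. Check the task program ("Experimental scripts will run in E-Prime") and the device presets, and correct whichever statement is wrong. If it is the trial count, correct the six/six split and the late-extinction rule as well.
2. State when active current ends in the during-extinction arm and when the second block starts in each arm.
3. For participants already treated, use the script and presets, plus existing session records where they show timing: the impedance forms and the continuous skin-conductance recordings. Section 3.D2 says the device itself produces no data beyond a contact-quality display.
4. For remaining sessions, log the start and stop of each block and the time of the last extinction trial. The holder of the unblinded codes, not the operator, derives active minutes per window. If block timing differs visibly by arm, the check of blinding adequacy should take that into account.
5. Report active minutes by window and arm, and word the after-versus-during conclusion to match. With overlap, do not read a null result as absence of a timing effect. With unequal doses, do not attribute a difference to timing alone. If only the text was wrong, correct the text.

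The cost is one check, a wording correction, some hand logging and possibly a narrower after-versus-during conclusion. Dose, task length and sample size are untouched.

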Transcranial direct current stimulation Procedures: Two conductive rubber electrodes will be inserted into reusable sponge pockets saturated with 0.9% normal saline and securely attached to the participant's scalp using a rubber headband prior to beginning the task on Day 4. To reduce the likelihood of side effects, the skin under the stimulation sites will be lightly cleaned with alcohol and inspected for lesions or abnormalities. Participants will be instructed to notify the experimenter of any discomfort. To ensure tDCS tolerability and condition the skin, all participants will receive brief stimulation (1 mA for 30

seconds, with a ramp up/down over 30 seconds each) prior to beginning the task. Impedance, indicating electrode contact quality, will be monitored and recorded throughout tDCS administration. tDCS (or sham) will start 2 minutes prior to extinction learning and will continue throughout the extinction learning phase. For participants randomized to tDCS after extinction learning, tDCS will start immediately after completion of the last extinction trial. We will evaluate tDCS tolerability and adequacy of blinding following task procedures on Day 4. Double-blinding of sessions (active vs. sham) will be achieved through the use of participant-specific blinding codes preset in the tDCS device. [name] (mentor) will generate and oversee unblinded codes. Side effects related to tDCS will be recorded using a tDCS side effects questionnaire, including but not limited to queries about skin discomfort, headache and dizziness based on Brunoni et al. (73), see Appendix.

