Regarding tDCS device instructions, the use of an electrically isolated power source (i.e., battery-powered DC stimulation device) protects against delivery of more intense currents than intended. These devices also feature a continuous visual indication of electrode contact quality during all phases, a clear indication of the actual current supplied at time of stimulation, and the ability to deliver sham stimulation for single and double-blind studies. Prior to active or sham tDCS, participants will be primed for stimulation by applying a 1 mA stimulation for 30 sec, with a ramp up/down over 30 sec each. Impedance of tDCS will be recorded and monitored throughout the session to be below 25 kΩ (which is well below the pre-determined factory device maximum of 55 kΩ). The proposed stimulation is within the typical range of intensity (1-2mA) and duration (up to 20 min) for tDCS administration. No serious adverse side effects have been reported in previous studies within our lab with the proposed stimulation settings. Prolonged passage of direct current across metallic electrodes (where electrons from the stimulator are converted to ions carried through the body) can produce undesired electrochemical products such as pH changes. Electrodes will be embedded into a specifically designed sponge pad moistened with normal, 0.9% saline which will act to physically separate, and thus buffer, the skin from electrochemical changes and maintain even current density over time.

Given our proposed stimulation parameters, the proposed tDCS protocol is considered conventional in that it meets current, duration and charge safety limits. In tDCS safety testing, subjects were exposed to current densities of up to 2.56 mA/cm², and durations of up to 22 minutes. No burns or significant discomfort occurred. In addition, electrodes will not be placed over skin lesions, such as vascular moles and angiomas that might have greater conductance than the surrounding skin, and the skin under the electrodes will not be abraded prior to stimulation. The safety of conventional tDCS has been recently published in a review by Bikson et al. (74). In the numerous tDCS studies performed in recent years, tDCS was associated most commonly with a mild tingling sensation (70.6% of 567 tDCS sessions in 102 subjects), moderate fatigue (35.3%), and a light itching sensation under the stimulation electrodes (30.4%). Headache (11.8%), nausea (2.9%) and insomnia (0.98%) were also reported, but fairly

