infrequently (75). However, the most serious adverse effect of tDCS consists of the formation of small circular skin burns under the electrodes (76-78). These studies have demonstrated that the risk for skin burns increases when the skin under the electrodes is vigorously abraded before stimulation (Loo et al., 2011) or tDCS is applied without an adequate skin buffer during multiple, consecutive tDCS sessions. Subsequent tDCS practices in which the skin was not abraded before stimulation and the use of sodium chloride solution or gel, together with replacement of deteriorated tDCS supplies (e.g. sponge pads or electrodes) have not resulted in skin burns. Hence, in this study we will 1) not abrade any skin before tDCS application, 2) always use normal saline to moisten the tDCS sponges in which electrodes are embedded, and 3) carefully inspect the electrodes and electrode holders for damage or wearing. In addition, given the reported case studies of hypomania in a course of daily tDCS application, we exclude participants with a history of bipolar disorder.

Other precautions will consist of instructing participants to inform the experimenters of any (increasing) discomfort during testing (as such discomfort may be an indication that skin burns could form with continued stimulation), inspection of stimulation sites as needed and immediate discontinuing stimulation if discomfort occurs. Instantaneously making or breaking of the stimulating circuit results in AC current transients that cause neuronal firing (47). This is noticeable as brief retinal phosphenes with electrodes near the eyes. Therefore, participants will be told in advance that if the tDCS stimulator needs to be turned off suddenly out of safety precautions, they may experience a one-time sensation of a brief light flicker (similar to a broken fluorescent light) due to the sudden offset of the device.

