To assess for presence and tolerability of adverse events, we will use the tDCS Adverse Effects Questionnaire, developed by Brunoni and colleagues (73). For tDCS procedures occurring at the Brown MRF, the principal investigator will be present in the room for the first five participants and onsite for future participants. For tDCS procedures occurring at Butler Hospital, physician with advanced training in Neuromodulation techniques will be immediately available for management of emerging events. [name], in the role as study physician/mentor, will also be available to supervise or consult on tDCS administration and will be available to consult on handling of any emergent events. If there is any doubt about the mental or physical status of an individual after testing, the supervising physician will be called to evaluate the participant and make a recommendation for follow-up care if that is required.

Prior to administering tDCS in this protocol, all staff involved in administration of tDCS will be required to undergo training and demonstrate competence in the safe delivery of tDCS. There are multiple components of training in order to be able to administer tDCS, including initial *didactic training* to introduce concepts critical to tDCS, direct *observation* of tDCS procedures, *practice* of the various steps of setting up/administering tDCS on non-patient volunteers, including role-plays of scenarios of when the covering physician should be consulted to further address adverse events related to the study protocol, and *demonstration of competency* in all aspects of relevant subject assessment and in administration of the entire tDCS procedure under direct observation of a qualified tDCS administrator.

tDCS will be administered by the tDCS Operator (Dr. [name] or the research assistant (TBD)). The tDCS Operator is trained in the use of tDCS devices and has knowledge of safety considerations and precautions associated with tDCS. Responsibilities include of the tDCS Operator include:

- A) Positioning or assessment of positioning of the tDCS device on the participant prior to initiating stimulation.
- B) Operation of or monitoring of the hardware associated with the tDCS device.
- C) Administration of tDCS, or monitoring thereof.
- D) Brief assessment of relevant mental status and general clinical condition before and after tDCS.

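### No structured tDCS side-effect assessment is scheduled after the Day 4 session, so delayed effects, chiefly insomnia, are not collected systematically although completers return 20 to 28 hours later

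*Combined protocol and SAP*

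**What the plan says.** Section C3 (tDCS procedures) dates the assessment: "We will evaluate tDCS tolerability and adequacy of blinding following task procedures on Day 4". It describes the instrument without a time point of its own: "Side effects related to tDCS will be recorded using a tDCS side effects questionnaire, including but not limited to queries about skin discomfort", followed by headache and dizziness. Section D1, item (5), restates it, again without a time: "To assess for presence and tolerability of adverse events, we will use the tDCS Adverse Effects Questionnaire". The operator's duties in the same item include "Brief assessment of relevant mental status and general clinical condition before and after tDCS", which belongs to the stimulation session.

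The final visit follows a day later: "Visit 5 will need to occur 24 hours after visit 4, with an allowable deviation of 4 hours". Its listed content is the retention and renewal tasks, contingency ratings, affect ratings and an optional scan. It closes as follows: "After fear renewal participants will complete contingency ratings and the PANAS to assess general affect". No side-effects form, sleep question or site inspection is listed.

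On what might be found, section D1, item (5), gives rates from earlier tDCS work: "Headache (11.8%), nausea (2.9%) and insomnia (0.98%) were also reported, but fairly" infrequently. It calls skin burns the most serious effect. Section C3 has the skin checked before stimulation. Among its other precautions, D1 item (5) lists "inspection of stimulation sites as needed".

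**The concern.** An effect on sleep needs a night to appear. A questionnaire completed within the Day 4 visit, which lasts about an hour, comes before that night. Sleep is otherwise measured only by the Pittsburgh index at Visit 1, before any stimulation. The plan therefore names an effect that its only dated assessment cannot reach. A headache or skin reaction that began after the participant left would also fall outside that form, although the documents do not say how often this happens.

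What is at stake is how the safety summary can be read. The trial has 100 participants assigned to active stimulation and 50 to sham only, and its stated long-term goal is to develop tDCS alongside exposure therapy. If later effects reach the record only when someone volunteers them, a low count partly reflects how the data were collected. Asking every participant the same question is what would allow a sleep complaint after active stimulation to be set against those after sham.

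**Working it through.** **Interval to the next visit.** Section C3 gives 24 h with a deviation of 4 h: 24 − 4 = 20 h and 24 + 4 = 28 h. Every completer is seen again after one intervening night.

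**Number exposed.** Section C2 has three groups of 50. Two receive one active session each: 2 × 50 = 100. Sham only: 50.

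**Denominator of the quoted rates.** Section D1, item (5), cites 567 sessions in 102 subjects. I tested which denominator gives the printed percentages from whole counts.

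| Effect | Printed | Out of 102 | Out of 567 |
|---|---|---|---|
| Headache | 11.8% | 12/102 = 11.8% | 67/567 = 11.8% |
| Nausea | 2.9% | 3/102 = 2.9% | 16/567 = 2.8% |
| Insomnia | 0.98% | 1/102 = 0.98% | 6/567 = 1.06% |

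Nausea and insomnia fit 102 and not 567, so the rates are best read as per subject.

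**Adjustment for exposure.** Those subjects averaged 567/102 = 5.6 sessions; this trial gives one active session. The upper end applies the per-subject rate unchanged, as if an affected subject were affected at every session. The lower end assumes that each affected subject was affected in exactly one session, so the rate per session is the subject count divided by 567.

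| Effect | Lower, in 100 active | Upper, in 100 active |
|---|---|---|
| Insomnia | 100 × 1/567 = 0.18 | 100 × 0.0098 = 0.98 |
| Headache | 100 × 12/567 = 2.1 | 100 × 0.118 = 11.8 |

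The chance of at least one insomnia case is 1 − (1 − p)^100:
- p = 1/567 gives 0.16
- p = 0.0098 gives 0.63

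With perfect ascertainment, no case at all would still have a probability of 37% to 84%.

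**Headaches starting after the Day 4 form.** Onset times are not given, so the late share is an assumption.

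| Assumed late share | Late headaches in 100 active |
|---|---|
| 10% | 0.2 to 1.2 |
| 25% | 0.5 to 3.0 |
| 50% | 1.1 to 5.9 |

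No rate is given for skin burns, so none is computed.

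**What a zero would mean.** If all 100 were asked and none reported insomnia, the one-sided 95% upper limit would be 1 − 0.05^(1/100) = 3.0%. A zero from volunteered reports supports no such limit, because the number effectively asked is unknown.

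**The case against.** The strongest reply is that other routes exist. Section D1, item (4), has all participants debriefed after completing the study and invited to raise discomfort from any point in it; for completers this follows Day 5. Section D3 has identified adverse events tracked and reviewed weekly, and the DSMB reviews all of them. A reader might infer that delayed effects cannot be recorded, or that nobody asks. The documents do not support that. What stands is narrower: the debrief sits under the fear-task risk, is open-ended, has no stated form and follows completion. Section C1 plans 180 inclusions for 150 completers, so about 30 may not reach it. The tracking in D3 handles events once identified and schedules no question after Day 4.

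A reader might also infer that the questionnaire is given only once. No sentence says so. The Appendix and the binder of operating procedures were not available and could hold a repeat, so the claim is limited to the visit schedule in the protocol.

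Nor does the protocol describe headache or burns as delayed. It treats burns mainly as something to detect during stimulation, and both the operator's duties and section D3 require observation for them. Only insomnia is late by its nature.

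Finally, safety is not one of the aims, this is a single-session laboratory study, and the expected counts are low. That is fair, and it limits the weight of the point.

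**Conclusion.** The point holds in a limited form, as a cheap improvement. The protocol's visit schedule has no structured tDCS side-effect assessment after Day 4. Insomnia is the clear gap; late headaches and skin reactions are possible but unquantified. Such effects can still enter the record, but unsystematically, so their absence would be weak evidence and a comparison of active with sham would be unreliable.

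The size is about 0.18 to 0.98 insomnia cases and 2.1 to 11.8 headaches of any onset among 100 active participants. This assumes that the quoted rates carry over to this population and montage, that they are per subject, and that the two exposure assumptions bracket the truth. The 63% chance of at least one insomnia case is the top of a range that starts at 16%, so it should not be read as a point estimate. At these counts a formal test of insomnia between groups would not be informative; the gain is a descriptive record with a known denominator.

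**What to change.** In the Day 5 text of section C3, repeat the existing tDCS side-effects questionnaire with one added item on sleep since Day 4. Give it alongside the closing affect ratings after fear renewal, when retention has already been measured and cannot be influenced. In the tDCS procedures and section D1, item (5), have a look at both electrode sites recorded for everyone at electrode removal on Day 4 and again at Visit 5. Telephone anyone stimulated on Day 4 who does not return and ask the same questions. Report the answers by randomized group with the number asked as the denominator.

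If the Appendix or the operating-procedures binder already schedules a repeat, it is enough to state that in the Day 5 schedule.

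The cost is a few minutes at an existing visit with an existing form, an occasional telephone call and a short amendment. The change concerns data collection only and alters no stimulation parameter or treatment rule.
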